7.2.2.5.1 Hematology

Hematology tests are to be performed as outlined in [Table 7-6](#) by the local laboratory according to the visit schedule outlined in [Table 7-1](#), [Table 7-2](#), and [Table 7-3](#).

7.2.2.5.2 Clinical chemistry

Clinical chemistry tests are to be performed as outlined in [Table 7-6](#) by the local laboratory according to the visit schedule outlined in [Table 7-1](#), [Table 7-2](#), and [Table 7-3](#). It should be noted in the patient's eCRF if the patient was fasting at the time of blood sampling.

7.2.2.5.3 Coagulation

[figure not shown]
Coagulation will be measured/calculated at screening. The schedule is outlined in [Table 7-1](#), [Table 7-2](#), [Table 7-3](#) and [Table 7-6](#).

7.2.2.5.4 Thyroid function

A full panel for thyroid function is required at screening (TSH, T3 [free] and T4 [free]). At other visits, only TSH is required unless the results are abnormal or it is increasing to an extent deemed clinically significant. Testing is to be performed as outlined in [Table 7-6](#) by the local laboratory according to the visit schedule outlined in [Table 7-1](#), [Table 7-2](#), and [Table 7-3](#).

7.2.2.5.5 Virology panel

Virology panel outlined in [Table 7-6](#) will be performed as per the assessment schedule in [Table 7-1](#), [Table 7-2](#) and [Table 7-3](#).

7.2.2.5.6 Serology panel

Serology testing may be done on remnant serum samples if a patient experiences an adverse event. The testing will be conducted by a central lab.

7.2.2.5.7 Pregnancy and assessments of fertility

A serum pregnancy test must be performed at screening, every month during the study and at the end of treatment visit. If the screening pregnancy test is performed within 72 hours of cycle 1 day 1, pregnancy test does not have to be repeated.

Every month during the safety follow-up period and at the end of the safety follow-up period, a serum or urine pregnancy test must be performed. If the patient is not coming to the clinic during the safety follow-up, it can be performed at home or at a local doctor's office, and the results will be communicated to the site staff. These follow-up pregnancy tests will be recorded only in the source documentation, not in the CRF.

A pregnancy test is only needed if the patient is a woman of child-bearing potential.

During the COVID-19 pandemic, if the patient cannot visit the site to have serum pregnancy tests done, locally available urine pregnancy test kits may be used. Relevant patients can perform the urine pregnancy test at home and report the result to the site. It is important that patients are instructed to perform the urine pregnancy test first and only if the test result is negative proceed with the administration of the study treatment. A communication process should be established with the patient so that the Site is informed of the pregnancy test results.

7.2.2.5.8 Urinalysis

Dipstick measurements for specific gravity, pH, protein, glucose and blood will be performed as outlined in [Table 7-6](#) and as indicated in [Table 7-1](#), [Table 7-2](#) and [Table 7-3](#). Any significant findings on dipstick will be followed up with a microscopic evaluation where Microscopic Panel (Red Blood Cells, White Blood Cells, Bacteria, and Epithelial cells will also be measured).

7.2.2.6 [For Japan only] Radiological examinations

7.2.2.6.1 Chest X-ray

A 2-view chest X-ray will be performed as outlined in [Table 7-1](#), [Table 7-2](#) and [Table 7-3](#).

7.2.2.7 Cardiac assessments

7.2.2.7.1 Electrocardiogram (ECG)

All ECG evaluations will be independently reviewed at central labs. Instructions for the collection and transmission of ECGs to the central ECG laboratory will be provided in the ECG Manual. A standard 12-lead ECG will be performed as per the assessment schedule in  at the same time point

should be taken after the ECGs are completed. The ECGs must be performed in triplicate, at least 1-2 minutes apart, as shown in the tables below.

Interpretation of the tracing must be made by a qualified physician and documented on the ECG CRF page. Each ECG tracing should be labeled with the study number, patient initials (where regulations permit), patient number, date, and kept in the source documents at the study site. Clinically significant abnormalities present at screening should be reported on the Medical History CRF page. Clinically significant findings must be discussed with Novartis prior to enrolling the patient in the study. New or worsened clinically significant findings occurring after informed consent must be recorded on the Adverse Events CRF page.

Table 7-7 Central ECG collection plan

Cycle	Day	Time	ECG Type
Screening	-21 to -1 days	Anytime during the screening period	12 Lead, triplicate
1	1	Pre-dose (baseline ECG) 2-hr post-NIR178 dose, ± 15 min	12 Lead, triplicate
1	7 (only required for Part 2 NIR178 Schedule 3)	Pre-dose 30 min, 1-hr, 2-hr, 3-hr, 4-hr post-NIR178 dose, ± 15 min	12 Lead, triplicate
1	14 (only required for Part 2, NIR178 Schedule 2)	Pre-dose 30 min, 1-hr, 2-hr, 3-hr, 4-hr post-NIR178 dose, ± 15 min	12 Lead, triplicate
1	28 (only required for Part 1 and Part 2 NIR178 Schedule 1)	Pre-dose 2-hr post-NIR178 dose, ± 15 min	12 Lead, triplicate
2 to 6	1	Pre-dose	12 Lead, triplicate
EOT	1	Any time	12 Lead, triplicate
Unscheduled	N/A	Any time	12 Lead, triplicate

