1.2.1.4.1 Clinical pharmacokinetics of NIR178

The pharmacokinetics of NIR178 both single and repeat dose of NIR178 has been characterized in healthy volunteers in prior studies as well as in NSCLC patients in an ongoing Phase I/Ib study (CNIR178X2103J). A mono-oxygenated metabolite (NJI765) was also monitored in healthy volunteer studies. In healthy volunteers, (single ascending dose levels of 10, 20, 40, 80, 160, 320 and 480 mg) NIR178 demonstrated rapid absorption and elimination with a Tmax of 0.17-4 hrs and a terminal elimination half-life of 1.06-3.83 hrs. Concentrations in the systemic circulation were generally below the lower limit of detection at 10 and 20 mg. Systemic exposure (Cmax and AUC) over the dose range of 40 to 480 mg generally increased more than proportionally with dose; inter-subject variability was moderate to high.

In the Phase I/Ib study in advanced NSCLC, patients were dosed NIR178 orally twice daily (BID) as a single agent 80, 160, 320, 480, and 640mg. NIR178 was rapidly absorbed with a median Tmax occurring at 2 hours post-dose. NIR178 featured nonlinear pharmacokinetics, both dose- and time-dependent. Similarly to healthy volunteers, NIR178 systemic exposure increased more than proportionally with dose following single and repeated BID dosing of 80 to 640 mg. Despite of its short terminal half-life, the accumulation ratio of NIR178 was approximately 3-fold after one week of multiple daily dosing compared to a single dose. Inter-subject variability in Cmax and AUC was moderate to high. The pharmacokinetics of NIR178 (160, 240, and 320 mg BID) when given in combination with PDR001 (400 mg every 4 weeks) in patients with advanced NSCLC is largely similar to that of NIR178 alone, suggesting no clinically relevant interaction between the two drugs.

Please refer to the [NIR178 (PBF-509) Investigator's Brochure] for further details.

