Grade 3 or Grade 4	Discontinue study treatment. Follow-up CRS as per institutional guidelines.
Ocular (uveitis, eye pain, blurred vision)	
Grade 1	Continue study treatment without dose modification. Ophthalmology consultation.
Grade 2	Hold study treatment. Urgent ophthalmology consultation. Upon resolution to ≤ Grade 1 may consider resuming study treatment without dose reduction after discussion with the Novartis Medical Monitor and in consultation with ophthalmology.
Grade 3 or Grade 4	Discontinue study treatment. Urgent ophthalmology consultation.

[figure not shown]
Worst toxicity CTCAE^a grade	Recommended Dose Modification
Pulmonary (pneumonitis)	
Grade 1	Consider study treatment hold. Manage per institutional practice, consultation with pulmonologist is recommended. Consider resuming study treatment upon radiographic evidence of improvement.
Grade 2	Hold study treatment. Pulmonary and infection workup, consultation with pulmonologist is recommended. Upon resolution to ≤ Grade 1, may resume study treatment without dose modification.
Grade 3 or Grade 4	Discontinue study treatment. Manage per institutional practice, consultation with pulmonologist is recommended.
<hr/>	
Cardiovascular	
ECG QTc-Interval prolonged; hypertension	
Grade 3	Hold study treatment. Upon resolution to Grade ≤ 1 or baseline (hypertension, QTc) or < 30 msec difference from baseline (QTc) within ≤ 7 days, may resume study treatment without dose modification after discussion with the Novartis Medical Monitor. Baseline ECG refers to the ECG(s) collected at screening.
Grade 4	Discontinue study treatment.
Other cardiovascular disorders	
Grade 2 (except myocarditis)	Hold study treatment. Upon resolution to Grade ≤ 1 or baseline, may resume study treatment without dose modification after discussion with the Novartis Medical Monitor.
Grade 2 myocarditis, or Grade ≥ 3 other cardiac disorders related to study treatment	Discontinue study treatment.

[figure not shown]
Worst toxicity CTCAE^a grade	Recommended Dose Modification
Gastrointestinal	
Diarrhea/colitis*	
Grade 1	May continue study treatment without dose modification. Manage per institutional standard guidelines which should include anti-diarrheal treatment, consideration of corticosteroid therapy, and hydration.

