7.1 Study flow and visit schedule

Table 7-1, Table 7-2 and Table 7-3 lists all of the assessments and indicates with an “X”, the visits when they are performed. Japanese safety run-in part will be conducted in accordance with Table 7-1. Part 3 visit schedule will be followed by the continuous BID visit schedule (Table 7-1).

All data obtained from these assessments must be supported in the patient’s source documentation. The table (“Category” column) indicates which assessments produce data to be entered into the clinical database (D) or remain in source documents only (S).

No CRF will be used as a source document.

Screening evaluations must be performed ≤ 21 days of Cycle 1 Day 1 (except for the pregnancy test which must be performed within 72 hours before day 1 of every cycle and baseline imaging assessment which should be performed ≤ 28 days of Cycle 1 Day 1). Assessments performed as part of the screening evaluations and within 3 days prior to the first dose of study treatment, are not required to be repeated on Cycle 1 Day 1. Laboratory and radiological assessments performed as part of standard of care prior to signing informed consent may be used if performed within the screening time window.

During the course of the study visits, tests and/or procedures should occur on schedule whenever possible. A visit window of +/- 3 days is allowed for assessments except Imaging and PK.

Imaging assessments have an on study visit window of ± 1 week, regardless of dosing schedule or possible dose delays.

On PK collection days, the time windows are provided in Table 7-8 to Table 7-11. In situations when dosing is delayed, PK collections should also be delayed until the subsequent dose is given.

If the COVID-19 pandemic limits or prevents on-site study visits, alternative methods of providing continuing care may be implemented. Phone calls, virtual contacts (e.g. teleconsult) or visits by site staff/home nursing service to the patient’s home depending on local regulations and capabilities, can replace on-site study visits, for the duration of the pandemic until it is safe for the patient to visit the site again.

Table 7-1 Visit evaluation schedule for patients in Part 1, Part 2 NIR178 S1 (NIR178 Schedule 1-BID continuous dosing), Part 3 and Japanese safety run-in

Visit Name	Category	Protocol Section	Screening	Cycle 1 ^c					Cycle 2		Cycle 3		Day 1 of Subsequent cycles	End of study treatment (EoT)	Follow up *
				1	2	8	15	22	28	1	15	1			

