1 (Cycle 2 for Japanese safety run-in patients) ^e	22	504 h (± 8 hr) post dose	PDR001
2	1	Pre-dose ^b of cycle 2 (0 h)	PDR001 and ADA ^a
3	1	Pre-dose ^b of cycle 3 (0 hr)	PDR001 and ADA ^a
3	1	1 hr (± 5 min) post end of C3D1 infusion dose ^c	PDR001
3	15	336 hr (± 8 hr) post dose	PDR001
4	1	Pre-dose ^b of cycle 4 (0 h)	PDR001 and ADA ^a
5	1	Pre-dose ^b of cycle 5 (0 h)	PDR001 and ADA ^a
6	1	Pre-dose ^b of cycle 6 (0 h)	PDR001 and ADA ^a
EOT ^d		Anytime	PDR001 and ADA ^a
Unscheduled		Anytime	PDR001 and ADA ^a

Cycle	Study day	Scheduled time point (Sampling window)	Analytes

Blood samples are to be collected from the arm opposite from infusion site, or alternatively, infusion site will need to be flushed with 10 mL of saline.
 
^a Immunogenicity (IG) (Anti-Drug [PDR001] Antibody): blood samples to be collected for anti-drug antibody together with PK samples
 
^b Pre-dose blood samples should be collected prior to start of infusion of any treatment
 
^c PDR001 sampling time is relative to the end of PDR001 infusion
 
^d A PK sample collection will occur at cycle 6 or EOT, whichever occurs first
 
Note: For Japanese safety run-in, PDR001 samples collection will begin from cycle 2 onwards.
 
^e As of protocol amendment 6, patients enrolled in the Japanese safety run-in part will receive NIR178 in combination with PDR001 starting at Cycle 1 and PDR001/ADA PK sample collections will begin at Cycle 1
			

Table 7-9 Pharmacokinetic blood collection log for NIR178: Part 1, Part 2, Part 3 (NIR178 Schedule 1), and Japanese safety run-in

Cycle	Day	Scheduled Time Point (h)	Analyte ^b
1	1	Pre-dose (0 h)	NIR178 and NJI765
1	1	15 min post-dose (\pm 5 min)	NIR178 and NJI765
1	1	30 min post-dose (\pm 5 min)	NIR178 and NJI765
1	1	1 h post-dose (\pm 5 min)	NIR178 and NJI765
1	1	1.5 h post-dose (\pm 5 min)	NIR178 and NJI765
1	1	2 h post dose (\pm 10 min)	NIR178 and NJI765
1	1	3 h post-dose (\pm 10 min)	NIR178 and NJI765
1	1	4 h post-dose (\pm 30 min)	NIR178 and NJI765
1	1	8 h post-dose (\pm 30 min)	NIR178 and NJI765
1	2	Pre-dose (0hr/12 hrs post day 1 evening dose)	NIR178 and NJI765
1	8	Pre-dose (0 h)	NIR178 and NJI765
1	15	Pre-dose (0 h)	NIR178 and NJI765
1	28	Pre-dose (0 h)	NIR178 and NJI765
1	28	15 min post-dose (\pm 5 min)	NIR178 and NJI765
1	28	30 min post-dose (\pm 5 min)	NIR178 and NJI765
1	28	1 h post-dose (\pm 5 min)	NIR178 and NJI765
1	28	1.5 h post-dose (\pm 5 min)	NIR178 and NJI765
1	28	2 h post dose (\pm 10 min)	NIR178 and NJI765

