2.6.2.6 Other safety data

2.6.2.6.1 ECG and cardiac imaging data

In case the study requires ECG replicates at any assessment, the average of the ECG parameters at that assessment should be used in the analyses.

12-lead ECGs including PR, QRS, QT, QTcF, QTcB, and RR intervals will be obtained centrally/locally for each patient during the study. ECG data will be read and interpreted centrally/locally.

The following summaries will be presented:

- Change from baseline for ECG parameters by timepoint
- Number and percentage of patients with notable ECG values.
 - QT, QTcF, or QTcB
 - New value of > 450 and ≤ 480 ms
 - New value of > 480 and ≤ 500 ms
 - New value of > 500 ms
 - Increase from baseline of > 30 ms to ≤ 60 ms
 - Increase from baseline of > 60 ms
 - HR
 - Increase from baseline >25% and to a new HR > 100 bpm
 - Decrease from baseline >25% and to a new HR < 50 bpm
 - PR
 - Increase from baseline >25% and to a new PR > 200 ms
 - New PR > 200 ms
 - QRS
 - Increase from baseline >25% and to a new QRS > 120 ms
 - New QRS > 120 ms

A listing of patients with only notable ECG values will be produced. For patients with at least one notable ECG parameter value, all parameters should be listed.

PK-ECG analysis

A linear mixed effects model will be used to analyze QTcF change from baseline versus plasma NIR178 concentration using the PK/ECG analysis set. The linear mixed effects model is as follows:

$$\Delta QTcF_{ij} = (\beta_0 + b_{0i}) + \beta_1 baseline_QTcF_i + \beta_2 concentration_{ij} + \epsilon_{ij}$$

In this model, b_{0i} is the patient's random effect. A compound symmetry covariance structure is assumed; other covariance structures may be explored.

The estimated mean QTcF change from baseline will be presented along with the two-sided 90% CI for different concentration thresholds (mean, Q1, median, and Q3) of C_{max} for dose levels 160mg BID and 240 mg BID, corresponding to C1D1 and/or steady state.

- These thresholds will be determined from C1D1 and/or steady state C_{max}
- Baseline QTcF will be set to its median baseline value

QTcF is suggested by the ICH E14 guidance (attached at the end of this document (Section 6)) and is more accurate than other correction methods in patients with altered heart rates. [REDACTED]

[REDACTED]

A check of mean concentration versus time and mean QTcF change from baseline versus time should be performed to rule out any delayed effect (hysteresis). [REDACTED]

[REDACTED]

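### Tables 7-1 and 7-7 contradict each other on ECGs for Part 3 and the Japanese run-in; if Table 7-7 is followed, neither group has an ECG scheduled near steady-state peak

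*Protocol*

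**What the plan says.** Protocol 7.1 places both groups under Table 7-1, titled "Visit evaluation schedule for patients in Part 1, Part 2 NIR178 S1 (NIR178 Schedule 1-BID continuous dosing), Part 3 and Japanese safety run-in". The text says the run-in is conducted according to that table and, for Part 3, that "Part 3 visit schedule will be followed by the continuous BID visit schedule". Its 12-lead ECG row has a mark at Cycle 1 Day 28 and on Day 1 of Cycles 2, 3 and all subsequent cycles. It gives no clock times.

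Protocol 7.2.2.7.1, Table 7-7, sets out the ECG collection plan with clock times. Its Cycle 1 Day 28 row is "28 (only required for Part 1 and Part 2 NIR178 Schedule 1", with a pre-dose set and a set at "2-hr post-NIR178 dose, ± 15 min". The Day 1 row covering Cycles 2 to 6 is pre-dose only, and no row covers Day 1 of later cycles.

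The PK log in Protocol 7.2.3 (Table 7-9) is headed "Pharmacokinetic blood collection log for NIR178: Part 1, Part 2, Part 3 (NIR178 Schedule 1), and Japanese safety run-in". It takes a full Day 28 profile, including a 2-h sample, with no exemption for either group.

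**The concern.** The two tables give a site different instructions for the two groups that Amendment 6 newly opens: patients on a tablet expected to improve bioavailability, and Japanese patients receiving 240 mg BID with PDR001 from Cycle 1. Drug levels build up, since Protocol 1.2.1.4.1 reports that "the accumulation ratio of NIR178 was approximately 3-fold after one week of multiple daily dosing compared to a single dose". An ECG after the first dose therefore cannot stand in for one at steady-state peak.

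At stake are direct QTc observations at the exposure of most interest. The protocol treats QTc as a monitored risk, with an entry exclusion, dose-modification rows and a ban on QT-prolonging drugs. Table 3-1 names ECG among the safety parameters for the run-in.

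**Working it through.** No power or error-rate calculation applies. The check sets the tables side by side.

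**Step 1. Table 7-1, read by column.** The ECG row has marks at Screening, C1D1, C1D28, C2D1, C3D1, Day 1 of subsequent cycles, and end of treatment (EOT). No footnote exempts Part 3 or the run-in from the Day 28 ECG.

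**Step 2. Table 7-7, on-treatment ECGs with a set timing, by group.**

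| Group | Cycle 1 | Cycles 2-6 Day 1 | Post-dose ECGs at or after one week of dosing |
|---|---|---|---|
| Part 1 | D1 pre and 2 h; D28 pre and 2 h | pre-dose | 1 |
| Part 2 Schedule 1 | D1 pre and 2 h; D28 pre and 2 h | pre-dose | 1 |
| Part 2 Schedule 2 | D1 pre and 2 h; D14 pre and five post-dose | pre-dose | 5 |
| Part 2 Schedule 3 | D1 pre and 2 h; D7 pre and five post-dose | pre-dose | 5 |
| Part 3 | D1 pre and 2 h | pre-dose | 0 |
| Japanese run-in | D1 pre and 2 h | pre-dose | 0 |

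All groups also have screening, EOT and unscheduled ECGs. The last two may be taken at any time.

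**Step 3. Where the remaining ECGs fall.** Protocol 1.2.1.4.1 gives a median Tmax of 2 h, so the 2-h ECG is a near-peak reading. In Part 3 and the run-in it occurs only after the first dose. With accumulation of about 3-fold, first-dose exposure is about 1/3 of exposure after a week. The protocol does not say whether the ratio refers to Cmax or AUC, so 1/3 is approximate for the peak.

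**Step 4. The PK half of the pair.** Table 7-9 takes the Day 28 2-h sample in both groups (window ±10 min). SAP 5.5.3 pairs an ECG with a PK sample when the two are within 15 minutes. Under Table 7-7 these groups have the sample but no scheduled ECG to pair with it.

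**Step 5. After Cycle 6.** Table 7-1 continues ECGs on Day 1 of every later cycle; Table 7-7 stops at Cycle 6. This difference affects every group under Table 7-1.

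**Step 6. Numbers affected by the Day 28 conflict.** Part 3 TNBC 20 to 30 (Protocol 10.8) plus Japanese 240 mg 3 to 6 (Protocol 4.1.4 and 10.8): 20 + 3 = 23 to 30 + 6 = 36 planned patients.

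**The case against.** The strongest reply is that the omission was intended. Amendment 6 cut ECG collection to a safety-monitoring level after time-matched sampling in 257 patients (244 at 160 mg, 13 at 240 mg), with two treatment-related QTc events, one Grade 1 and one Grade 2. That explains a general reduction but not this gap. The reduced plan keeps the Day 28 2-h ECG for Part 1. It also keeps five post-dose ECGs each for Schedules 2 and 3 of Part 2, which was already closed to enrolment. The supporting data, as of 3 August 2020, predate the tablet, and the six Japanese patients treated by then had received 80 or 160 mg. Nothing says that Part 3 or the run-in is exempt, or that either was once listed and then removed.

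A second reply has some force. The tablet was given only at 160 mg (SAP Section 4). If the dog ratios carried over and exposure were proportional to dose, 160 mg as tablet would match about 160 × 8,110/6,940 = 187 mg of capsule by AUC and 160 × 4,770/3,410 = 224 mg by Cmax. Both are below the 240 mg capsule dose, for which Part 1 has the Day 28 2-h ECG. This is indirect reassurance resting on two assumptions, and it does not resolve the contradiction.

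A reader might also infer more than the documents support:

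- That no ECG is taken near steady-state peak. This holds only if Table 7-7 prevails. Table 7-1 alone would give a Day 28 ECG, untimed, and an EOT or unscheduled ECG could fall near the peak by chance.
- That the dose decisions rest on these ECGs. The Part 3 rule counts related Grade 3/4 adverse events. The Japanese decision uses DLTs and a review of all available safety, PK and PD data.
- That the SAP steady-state estimate is lost. The model in SAP 2.6.2.6.1 reports "for dose levels 160mg BID and 240 mg BID, corresponding to C1D1 and/or steady state", not by formulation, and Part 1 and Part 2 can supply steady-state pairs.
- That the pre-dose ECGs see almost no drug. Healthy-volunteer half-lives of at most 3.83 h would give 2^(-12/3.83) = 0.114 of peak at 12 h. The same one-compartment reasoning predicts accumulation of only 1/(1 - 0.114) = 1.13, not about 3, so that fraction cannot be relied on.
- That the ECG baseline is ambiguous. Table 6-2 says "Baseline ECG refers to the ECG(s) collected at screening" for its rule on resuming treatment, while Table 7-7 and SAP 2.1.1.4 point to the pre-dose ECG for analysis. These are different uses.

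**Conclusion.** The contradiction is real and can be seen on the page. Table 7-1 requires a Day 28 ECG in Part 3 and the Japanese run-in; Table 7-7 leaves both groups out. The tables also differ for all their shared groups after Cycle 6. If Table 7-7 is followed, 23 to 36 planned patients have no ECG scheduled near steady-state peak, and their Day 28 2-h PK samples have no scheduled ECG to match.

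The conclusion assumes that a site lets Table 7-7 decide, which is plausible because only that table gives times. The readable text does not say which table takes precedence. The loss is of direct QTc observations in two small groups. It does not invalidate the dose decisions or the planned PK-ECG model. The item should be corrected because the inconsistency concerns a safety assessment and is easy to remove.

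**What to change.** Reconcile the two tables, in one of two ways:

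- To match Table 7-1, add Part 3 and the Japanese safety run-in to the Day 28 row of Table 7-7, with the pre-dose and 2-h timings that row already gives for Part 1. Table 7-1 itself carries only an untimed mark.
- Otherwise, state why these groups are exempt on Day 28 and remove the mark for them in Table 7-1.

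In either case, give one answer on ECGs after Cycle 6.

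The first option adds two triplicate sets per patient: 2 × 3 = 6 tracings, or 138 to 216 over 23 to 36 patients. The Day 28 visit and PK profile are already planned, and run-in patients are in hospital during Cycle 1. The second option costs only text.

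The SAP reports that the study is being closed out. If the protocol can no longer be amended, the study report should say which table sites followed and how many patients in each group have a Day 28 ECG.
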